5.4 Treatment Delivery

The population that is eligible for this study would not be eligible for RSBY under the program's usual rules. To make this study possible, we exchanged letters of cooperation with the state in which we conducted the study (Karnataka), the central government agency (Ministry of Labor) responsible for administration of RSBY, and the development organization (GIZ) providing technical support for RSBY.

Sample households were randomized in August 2014 using data from the listing exercise. They were informed of their treatment assignment and, depending on which arm to which they are assigned, given access to insurance or cash in May and June 2015. This step took place roughly 18 months after the baseline due to government constraints. Due to challenges associated with evaluating a government program, we were only able to enroll sample households when the government held its RSBY enrollment drive in early 2015.

We enrolled study households much in the same way the government enrolled RSBY (non-study) eligible households into the program: via a mobile enrollment truck that visited each village. One difference is that we went to each household to ask them if they would like to enroll and took them to the enrollment truck, which was parked in one place in the village. By contrast, the government informed non-study households by delivering paper notices (chits) to each home about when and where the enrollment truck would be in the village.

Roughly 78.4%, 70.4% and 58.6% of households in arms A, B, and C, respectively enrolled in RSBY. Enrollment rates are somewhat higher in Gulbarga than Mysore: 77.9/76.4/64.1% v. 78.8/63.5/52.3% in A/B/C. No one in arm D enrolled.

For all study households that take up insurance, we paid the government their premiums. For households in arms A, this was funded by grant funds. For those in B and C that purchase insurance, this was funded by the respondents' money.

The Karnataka government renewed RSBY automatically for non-study and study households in 2016 and 2017 without any action—even payment—by enrollees. RSBY ended in the state on August 31, 2018, to make way for the new NHPS scheme, which is scheduled to start in late 2018 or early 2019. As of this writing, Karnataka had agreed to roll out NHPS but had not begun the roll-out.

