7.3 Testing for heterogeneous effects

We will examine whether the impact of access to insurance and uptake into insurance varies with certain individual, household and village characteristics at baseline and enrollment. We will estimate these heterogeneous treatment effects as follows. We will interact the characteristics with household and village group indicators. For example, for ITT estimates and heterogeneous impacts from household-level treatments, the estimated equation would be:

$$\begin{aligned} y_{ijt} = & \alpha + \sum_{v=1}^3 \beta_v \sigma_j^v + \sum_{h=1}^3 \gamma_h d_{ij}^h + \sum_{h=1}^3 \sum_{v=1}^3 \lambda_{hv} \sigma_j^v d_{ij}^h \\ & + \sum_{v=1}^3 \beta_{vw} \sigma_j^v w_{ij} + \sum_{h=1}^3 \gamma_{hw} d_{ij}^h w_{ij} + \gamma_w w_{ij} + \sum_{h=1}^3 \sum_{v=1}^3 \lambda_{hvw} \sigma_j^v d_{ij}^h w_{ij} \\ & + \phi w_{ij} + \delta X_{ij} + e_{ijt} \end{aligned} \quad (4)$$

where w_{ij} is the continuous or binary characteristic along which we want to test heterogeneous impacts. The test for heterogeneous treatment effects along w_{ij} is whether we can reject $(\beta_{vw} = \beta_v, \gamma_{hw} = \gamma_h, \lambda_{hvw} = \lambda_{hv}) \forall (h, v)$. In order to ease interpretation, we will make modifications to the above specification analogous to the ones we make to ease interpretation of the ITT regressions.

We will test for heterogeneous treatment effects in two steps. First, we will test for heterogeneity along several basic dimensions¹³ we think are the most likely to generate heterogeneous effects:

1. District
2. Size of household
3. Age
4. Wealth (measured by assets)
5. Number of hospitals nearby or distance to closest hospital
6. Hospital utilization in prior year (measured at baseline)

¹³As noted above, for time-varying characteristics we will use the baseline values.

7. Monthly expenditure budget (measured at baseline)
8. Predicted propensity to utilize inpatient healthcare (described below)
9. Village size
10. Urban status

Second, we will use machine learning methods to help predict which dimensions of heterogeneity (from the list below) are most important (Duflo 2018, [Wager and Athey \(2018\)](#)).

1. District
2. Size of household
3. Cast or religion
4. Number of adults in household
5. Number of kids in household
6. Having children
7. Distance from closest public and/or private hospital
8. Number of public and/or private hospitals nearby
9. Presence or number of private hospitals nearby
10. Gender of subject

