11. Age or child/adult status
12. Marital status, birth order and relationship to household head
13. Size of village
14. Percent of village assigned to access to RSBY via this RCT
15. Percent of village eligible for RSBY outside the RCT
16. Hospital utilization in prior year (measured at baseline) or predicted hospitalization
17. Health status or serious sickness
18. Cognitive capacity
19. Willingness to pay for insurance (predicted based on data from a randomly selected sample of households removed from main RCT and chosen to participate in a WTP study)
20. Risk and time preferences
21. Assets and savings
22. Urban, peri-urban, and rural status
23. Monthly expenditure budget
24. Experiencing a serious health shock in the past year (provided this is balanced across treatment arms)

Predicting utilization. A natural dimension along which the impact of insurance may differ is the latent propensity of a household to experience health shocks which would require inpatient care. Since this variable is latent, it must be estimated. We will machine learning methods to predict households' likelihood to experience an inpatient hospitalization. We will perform this exercise on two samples: the baseline data (across all treatment arms) and the post-intervention data (using only group D, the control group). The resulting model will then be used to generate predictions for the full sample. Our key hypotheses are (1) that the impact of the offer of insurance will lead to larger treatment effects for those with higher propensity; and (2) that demand for insurance will be less price-elastic among those with higher propensity (i.e., adverse selection). Hypothesis (2) will be tested by examining how takeup of insurance varies between free and not free (group A vs. groups B and C) for high- vs. low-propensity households.

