10.2 Selection

We test this explanation by testing its assumptions or predictions:

- Individuals who were differentially sick or risk averse at baseline are more likely to enroll in RSBY in the first place and/or retain the RSBY card at midline and endline, conditional on household group assignment.
- Total utilization should be weakly higher in household group A than C. Equivalently, average utilization including both enrollees and non-enrollees, i.e., the ITT estimates of utilization, should be higher in A.¹⁹
- After predicting those in group A likely to enroll if they were in group C, we test to see if they have higher utilization conditional on getting insurance.

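### The only stated test of key hypothesis (2), adverse selection, compares high- with low-propensity households at an undefined cut, although the hypothesis is a gradient and every household has a continuous score.

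*Combined protocol and SAP*

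**What the plan says.** Under the paragraph on predicting utilization in section 7.3, machine learning is used to estimate each household's chance of an inpatient stay. Two versions of the score are planned: "We will perform this exercise on two samples: the baseline data (across all treatment arms) and the post-intervention data", the second fitted in group D only. Every household then has a score: "The resulting model will then be used to generate predictions for the full sample".

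Key hypothesis (2) is worded as a gradient: "that demand for insurance will be less price-elastic among those with higher propensity (i.e., adverse selection". The one test given for it is "examining how takeup of insurance varies between free and not free (group A vs. groups B and C) for high- vs. low-propensity households". The plan states no cut-point, regression or reason for grouping.

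The same section lists the score among the first-step modifiers for equation (4), as "Predicted propensity to utilize inpatient healthcare (described below". It says of the modifier in that equation that it "is the continuous or binary characteristic along which we want to test heterogeneous impacts".

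Section 5.4 already reports the outcome by arm: "Roughly 78.4%, 70.4% and 58.6% of households in arms A, B, and C, respectively enrolled in RSBY".

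**The concern.** Two things are at stake.

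- **Power.** Cutting a continuous score into two groups discards the variation within each group. If sensitivity to price falls steadily as predicted risk rises, the two-group test misses real adverse selection more often than a test on the score itself.
- **Open choices.** The line between high and low is not drawn, and nothing says which of the two score versions is used. Enrolment took place in 2015 and its rates by arm appear in the plan. For this hypothesis the outcome is therefore in hand before the analysis choices are fixed, and the answer may depend on where the line falls. That weakens the commitment a pre-analysis plan is meant to provide, whatever the size of the power loss.

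**Working it through.** The plan gives no power, effect size, score distribution or cut for hypothesis (2), so there is no figure of its own to reproduce. Its one power statement (section 5.1) concerns hospitalisation rates.

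**Inputs from the documents**
- 11,089 randomised households, with 40% in A and 20% in each of B and C (section 5.2 and Table 1). This gives 0.40 × 11,089 = 4,436 in A and 4,436 in B and C together.
- Take-up of 78.4% in A, and (70.4 + 58.6)/2 = 64.5% in B and C (section 5.4).

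**Assumptions**
- Two-sided 5% test, because the plan states sidedness only for spillover tests.
- An interaction linear in the score, except where a step is stated.

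**Step 1: precision of the continuous test.** Per SD of score, before any design effect,

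SE = √(0.784 × 0.216/4,436 + 0.645 × 0.355/4,436) = 0.0095.

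Power of 80% needs a non-centrality of 1.96 + 0.84 = 2.80, which is an interaction of 2.80 × 0.0095 = 0.0265, or about 2.65 points of take-up per SD. With an assumed design effect of 2 it is 0.0265 × √2, or about 3.75 points.

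**Step 2: effect of a split.** Under a linear interaction, a split multiplies the non-centrality by r, the correlation between the score and the high/low indicator. The share of information kept is r². Power is Φ(r × 2.80 − 1.96) + Φ(−r × 2.80 − 1.96).

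For a normal score cut at the median, r² = 2/π = 0.637 and r = 0.798. The non-centrality is 2.80 × 0.798 = 2.235 and power is 61%.

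| Assumed score and cut | Information kept | Power (continuous test 80%) |
|---|---|---|
| Bimodal, median | 0.94 | 78% |
| Uniform, median | 0.75 | 68% |
| Normal, median | 0.64 | 61% |
| Beta(2,18), median | 0.59 | 58% |
| Normal, top quartile | 0.54 | 54% |
| Lognormal (σ = 0.8), median | 0.37 | 40% |

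**Step 3: dependence on effect size.** For a normal score cut at the median, using the SE from step 1:

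| Interaction, points per SD | Continuous | Split | Loss, points | Loss with design effect 2, points |
|---|---|---|---|---|
| 1 | 18% | 13% | 5 | 2 |
| 2 | 56% | 39% | 17 | 10 |
| 2.5 | 75% | 56% | 19 | 14 |
| 3 | 89% | 71% | 17 | 18 |
| 4 | 99% | 92% | 7 | 18 |
| 5 | 100% | 99% | 1 | 12 |

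The loss is largest where the continuous test has about 75 to 80% power and fades for very small or very large effects.

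**Step 4: the reverse case.** If the truth is a step exactly at the median of a normal score and the split has 80% power, the linear term has a non-centrality of 2.80 × 0.798 and 61% power.

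**Step 5: does equation (4) already supply the test?** It admits a continuous modifier, but the heterogeneity test written beneath it is joint over all arms and shares: 3 + 3 + 9 = 15 restrictions. Suppose the whole signal lies in one contrast that a 1-df test detects with 80% power. The chi-square non-centrality is then 2.80² = 7.85, and a 15-df test has about 35% power. The targeted one-coefficient test is not laid down.

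**The case against.** The strongest reply is that the cut is inferred. Section 7.3 mentions no threshold, median or binary variable, and high versus low may be loose description of a gradient. The score is a listed modifier, take-up in 2015 is a listed outcome (section 8.1.1), and equation (4) accepts a continuous modifier. This stands in part: the plan does not require dichotomisation, and a continuous analysis is open under it. But the only test attached to hypothesis (2) is the two-group comparison, and step 5 shows that the test written for equation (4) is no substitute.

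A second reply is that the choice is partly a modelling preference, because a step at the cut reverses the ranking by about the same margin. That also stands, and the cost should be stated openly. However, the hypothesis is worded as a gradient and no cut is given at which a step would be expected.

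A reader might infer three stronger claims that the documents do not support:

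- **That the plan loses about 20 points of power, or at least a third of the information.** This needs roughly a normal score, a median cut and an effect near 80% power. A uniform score loses a quarter of the information and 12 points.
- **That section 10.2 suffers a calculable loss.** It says "After predicting those in group A likely to enroll if they were in group C, we test to see if they have higher utilization", but gives neither a probability cut-off nor the spread of predicted enrolment. Any power figure there would rest on invented inputs.
- **That a missed effect here leads to a wrong choice among the explanations in section 10.** Hypothesis (2) is not one of the 10.2 tests, so that route is not shown.

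**Conclusion.** The point holds as a request to name the test. Section 7.3 gives a graded hypothesis a two-group test with an undefined cut, and leaves two score versions in play when take-up by arm is already known. The openness of those choices follows from the text alone.

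The power loss is conditional on a linear interaction, a two-sided 5% test and an assumed score distribution. Where the continuous test has 80% power, a median split has 61% for a normal score and 68% for a uniform one. Across the assumed shapes and cuts tabulated, the loss runs from about 2 to 40 points. For a normal score cut at the median, it falls to about 1 point when the interaction is 5 points per SD with no design effect. None of these figures is a property of the plan.

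**What to change.** In section 7.3, replace the high/low test with wording such as: hypothesis (2) will be tested by the coefficient on not free (B or C versus A) × predicted propensity in the take-up regression, with propensity entered as a continuous score and village-clustered HC2 errors, as in section 7.1. In addition:

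- name one of the two score versions as the one used for this test;
- fix one scale in advance, raw probability or log-odds, because the two give different tests when the score is skewed;
- show take-up by propensity group, for example quartiles, as description only.

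As an optional clarification for consistency, the third test in section 10.2 could use the continuous predicted probability of enrolling under C.

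The change costs a few sentences and no new data. Its downside is the step case: about 61% power against 80% for a split placed exactly at the step. The grouped display keeps such a pattern visible.

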7.4 Accounting for multiple inference

Access to health insurance may affect a number of aspects of households' lives (such as health behaviors, health outcomes, investment decisions, and so on). When testing hypotheses about the impact of treatment on individual outcomes, no multiple testing adjustment is required.

However, our survey instrument in many cases includes multiple questions related to a single behavior or dimension. When those multiple questions are used to test a common hypothesis about a behavior or dimension, an adjustment is required. We will account for multiple inference when testing such hypotheses by using indices of outcome variables and family-wise p -value adjustment.

To be more specific, we have listed in Section 8 the primary groups of outcomes that we intend to consider. For each of these groups, we will construct indices (à la Kling, Liebman, and Katz (2007)) of all the outcomes in the family taken together. Then, for each of these index outcomes, we will report both the standard p -value and the p -value adjusted for multiple hypothesis testing across all the indices. We will calculate the adjusted p -values using the step-down procedure of Hochberg (1988), which controls the family-wise error rate for all the indices. (This is the approach taken in, for instance, Banerjee et al. (2015).)¹⁴

7.5 Minimizing attrition bias

We address the possibility that attrition affects our ITT or CATE estimates in the following manner. Let a_{ijk} be an indicator that equals 1 if our data contain a non-missing observation on household i in village j at baseline but not at endline. First, we check balance in attrition across household or village treatment arms by estimating the ITT model in equation (2) while setting $y_{ijt} = a_{ij}$. We will also test whether there is differential attrition across insured and uninsured households by estimating system (3) while setting $y_{ijt} = a_{ij}$.

Second, if we find evidence of differential attrition, we will take either of two approaches. One is to impute outcomes for attrited households using multiple imputation (King et al. 2001). In this approach, we will compare ITT and CATE effects with imputation and without. The other approach is to bound our parameter of interest using Lee bounds (Lee, 2009).

If we observe differential attrition, we will estimate all of our regressions with a correction for sample selection inspired by DiNardo, Fortin, and Lemieux (1996). Their procedure re-weights the data using the inverse of the propensity to be observed at endline, so that the distribution of observable characteristics at baseline among households observed at endline resembles that in the entire baseline sample.

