5.1 Sampling Strategy

The inclusion criteria for a household to be eligible for the study was that, at the start of the study in 2013:

1. The household resided in Gulbarga or Mysore district;
2. The household resided within 25 km of a hospital empaneled in RSBY; and
3. A member of the household must hold an Above Poverty Line (APL) ration card.

The exclusion criteria for the study were:

⁶They can be found at <http://www.rsbyp.gov.in/Documents.aspx?ID=4>

1. The possession of a BPL card;
2. Having a member working in one of the occupations that made the household eligible for RSBY regardless of BPL status; or
3. Having insurance that covered secondary hospital care (most commonly, Yeshasvini).

The two districts we selected were representative of central and southern India, respectively. We focused on APL households because they were treatment naive: they were not otherwise eligible for RSBY. The set of all household that met these inclusion criteria was larger than the target sample size for the study. Therefore we restricted enrollment to 25 km around a subset of hospitals in each district. We also omitted villages with ≤ 10 eligible households as the amortized fixed costs of reaching those households were very high.

The RCT was powered to detect a 25% change in hospitalization rate across study arms, allowing for a 10% attrition rate.

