5.2 Treatment assignment

We designed a two-stage randomization process to study both direct treatment and spillover effects of health insurance.

In a first stage, we randomly assigned villages to one of five village-level arms. A village-level arm is defined by the percentage of households within the village assigned to each of the four household-level study arms defined in subsection 4.2.1. The percentage allocations to the 4 household-level arms are given in the last 4 columns of Table 1. The percent of villages assigned to each of the 5 village-level arms are in the second column. Villages were matched before this first stage randomization.⁷

Table 1: IHIE Two-Stage Randomization Design

Village-level arms (%)		Household-level arms (%)			
Arm	Village allocation	Group A	Group B	Group C	Group D
I	15	30	50	10	10
II	15	30	10	50	10
III	15	30	10	10	50
IV	35	70	10	10	10
V	20	10	30	30	30
Total	100	40	20	20	20

In a second stage, we randomly assigned households within a village to the four arms according to the allocation probabilities assigned to the village. Households were matched before this second stage randomization.⁸

The target enrollment for each of the 4 household-level arms, unconditional on village-level arm, was 4,500 households for condition A and 2,250 households for each of conditions B, C and D. Due to some attrition between listing and completion of baseline, our final randomized sample amounted to 11,089 households in 424 villages in the two districts.

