5.6.2 Midline attrition

Attrition between baseline and midline can be attributed to household non-response and the inability to locate sample households, including their movement outside the village. Since many households with missing baseline data were able to be surveyed at midline, a total of 10,111 randomized households have midline data, an attrition rate of 7% between randomization and midline.

6 Companion willingness-to-pay study

We conducted a Willingness-to-Pay study (WTP study) that is distinct from but complements the main experiment. In some of our specified analyses, we will use the data from this companion study.

After conducting the listing exercise explained in Section 5.3.1, we selected a random subsample of 210 households, 105 from each district, to participate in the WTP study. Each of these households met the inclusion and exclusion criteria laid out in Section 5.1. However, these households were then excluded from selection for the main study, i.e., the treatment assignment described in Section 5.2. Instead, these 210 households were administered the baseline survey and a survey that used the Becker-DeGroot-Marshak (BDM) mechanism to measure the household's willingness to pay for RSBY health insurance. (These elicitations were incentivized, i.e., those households whose stated WTP was above the random draw in the BDM procedure received RSBY coverage at their stated WTP.)

7 Identification Strategy

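### Every attrition correction depends on an undefined check of attrition rates that has limited power for small gaps and cannot show whether the arms lose different kinds of households

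*Combined protocol and SAP*

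**What the plan says.** Section 7.5 defines an indicator for households observed at baseline but missing at endline. It uses this indicator as the outcome in equation (2), to compare attrition across arms, and in system (3), to compare insured with uninsured households. Then, "if we find evidence of differential attrition, we will take either of two approaches": multiple imputation, shown against the unimputed result, or Lee bounds. The next paragraph adds: "If we observe differential attrition, we will estimate all of our regressions with a correction for sample selection", by inverse-propensity weights built on baseline characteristics.

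The section gives no significance level, no choice between a joint test and single coefficients, and no size of gap that counts as evidence. It plans no attrition sensitivity analysis if the check is negative.

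The only effect size in the plan is in section 5.1: "The RCT was powered to detect a 25% change in hospitalization rate across study arms, allowing for a 10% attrition rate". The base rate, significance level, power and intracluster correlation behind it are not stated.

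**The concern.** A check that does not reject is not evidence that attrition is harmless, yet under section 7.5 it leaves the unadjusted estimate standing alone. Two things can go wrong. A real gap in attrition can be missed because it is small relative to its standard error. Or the arms can lose equal shares of households that differ in health or finances, which no comparison of rates would show.

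Loss related to outcome is plausible here. The endline comes four years after treatment, section 5.6.2 lists moving out of the village as a cause of loss, and mortality is itself an outcome in section 8.4. When the check is positive, the plan does not say whether imputation or bounds will be reported, although its stated purpose is to commit to the analysis before endline data are obtained.

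**Working it through.** **The plan's own figures.** The 25% design figure cannot be reproduced, because its base rate, significance level, power and clustering allowance are not given. Section 5.6.2 reports "a total of 10,111 randomized households have midline data, an attrition rate of 7% between randomization and midline". The counts give 1 − 10,111/11,089 = 8.8%. Figure 1 is not available, so another denominator may explain the 7%. Both values are close to the 10% allowed for, so 10% is used below as the lower arm's attrition.

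**Inputs.** Section 5.2 gives 11,089 randomised households in 424 villages, and Table 1 allocates 40/20/20/20%. That is 0.40 × 11,089 = 4,436 in A and 0.20 × 11,089 = 2,218 in each of B, C and D. Assumed: a two-sided 5% test, and a design effect of 1 or 1.5.

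**Step 1. Power of a simple comparison of attrition rates.** Power = Φ(d/SE − 1.96), where d is the gap.

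- C v D, 10% v 12%: SE = √(0.10×0.90/2,218 + 0.12×0.88/2,218) = 0.00939. Then 0.02/0.00939 = 2.13, and power = Φ(0.17) = 57%.
- Same, design effect 1.5: SE = 0.00939 × √1.5 = 0.0115. Power = Φ(1.74 − 1.96) = 41%.
- A v D, 10% v 12%: SE = √(0.10×0.90/4,436 + 0.12×0.88/2,218) = 0.00824. Power = Φ(2.43 − 1.96) = 68%, or 70% with a pooled variance.
- C v D, 10% v 11%: SE = 0.00920. Power = Φ(1.09 − 1.96) = 19%.

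At about 10% attrition without clustering, 80% power needs a gap of about 2.5 points for C v D and 2.2 points for A v D.

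This is simpler than the check the plan names. Equation (2) as printed has 4 + 3 + 12 = 19 treatment terms. The four shares sum to 1, so each arm's four interactions add up to that arm's indicator. Only 16 terms are independent, and the arm coefficients need a normalisation that the plan does not state. In a simulation of 424 villages of 26 households (intracluster correlation 0 and 0.05), a joint 12-degree-of-freedom test of the full model detected a 2-point excess in D about 35% of the time. A model without interactions detected it about 52–61% of the time. Power therefore depends on a rule that is not written down.

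**Step 2. Bias from a missed gap.** Let a be attrition in the arm that loses more, m the outcome rate among its excess leavers, and p the usual rate. The shift among completers is [d/(1 − a)] × (m − p). For 10% v 12%, d/(1 − a) = 0.02/0.88 = 0.0227.

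Worst case, every excess leaver hospitalised (m = 1), over assumed base rates:

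| Base rate p | Largest shift | 25% change sought |
|---|---|---|
| 5% | 0.0227 × 0.95 = 2.2 points | 1.25 points |
| 10% | 0.0227 × 0.90 = 2.05 points | 2.5 points |
| 20% | 0.0227 × 0.80 = 1.8 points | 5.0 points |

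In the other direction (m = 0), the shift at p = 10% is 0.0227 × 0.10 = 0.23 points.

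Moderate selection, with leavers at k times the usual rate: relative bias = 0.0227 × (k − 1). This is 2.3% at k = 2 and 4.5% at k = 3. For a 2.5-point gap (10% v 12.5%) the factor is 0.025/0.875 = 0.0286, giving 2.9% and 5.7%. Matching the 25% sought at a 2-point gap needs k − 1 = 0.25/0.0227 = 11, so leavers at about 12 times the usual rate. Since m cannot exceed 1, that is possible only if p is at or below 1/12 = 8.3%.

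**Step 3. Equal attrition, different leavers.** With 10% lost in each arm, the relative bias is (0.10/0.90) × (difference in k between arms). It reaches 25% when that difference is 0.25 × 0.90/0.10 = 2.25. The rates are then identical, so a test of rates has nothing to find.

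**The case against.** The strongest reply is that the harm is small. A reader might infer that the check can easily miss a gap whose bias is as large as the effect sought. The documents do not support that: they give no hospitalisation rate, and step 2 shows that it takes a base rate of about 8% or less with every excess leaver hospitalised. Under moderate selection, the bias from a missed 2-point gap is under a fifth of the 25%.

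Second, C v D is the least favourable contrast, and households were randomised within villages, so village effects largely cancel. With equal villages of 26, the C v D design effect is about 1 + 2.1 × ICC, or 1.11 at an ICC of 0.05, and power at a design effect of 1.1 is 53%. Reaching 1.5 needs an ICC of about 0.24, or about 0.10 if village sizes vary strongly. The 41% is therefore towards the pessimistic end. Reading the check from single arm coefficients of the interacted model would make it look much weaker, but the plan does not say it will be read that way, and section 7.1 drops the interactions for some reports.

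Third, a reader might infer that the correction can be chosen freely on the result. That goes too far. Once triggered, re-weighting applies to all regressions, and imputation must be shown beside the unimputed estimate. Only the choice between imputation and bounds is open.

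Fourth, the usual remedies do not repair equal-rate selection: Lee bounds trim nothing when rates are equal, and re-weighting adjusts only for what was observed. This stands as a limit on the fix. Nor can the documents show whether attrition has differed by arm so far, since Figure 1 is not available.

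None of this removes the main point: all three corrections wait on a check with no stated rule, and none is planned if it is negative.

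**Conclusion.** The point holds in a limited form. Section 7.5 makes imputation, Lee bounds and re-weighting all conditional on a check with no decision rule. For a 2-point gap at about 10% attrition, a simple comparison has 57% power for C v D and about 70% for A v D without clustering. These figures assume a two-sided 5% test; the 41% also rests on an assumed design effect of 1.5. The check is blind to differences in who leaves.

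The worst-case shift from such a gap exceeds the effect sought at a 5% base rate, is about four-fifths of it at 10% (2.05/2.5 = 82%), and is just over a third at 20% (1.8/5.0 = 36%). Moderate selection gives about 2–6% relative bias. This is a reason to report the corrections routinely, not a finding that the main estimates are likely to be badly biased.

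**What to change.** Remove both conditions from section 7.5. For A, B and C versus D, on the index outcomes and hospitalisation, always report the re-weighted estimate and Lee bounds beside the unweighted estimate. Keep multiple imputation as a further sensitivity analysis, so that no choice between it and the bounds remains. Report the attrition-rate test as description, with a by-arm comparison of leavers' baseline characteristics, which addresses what the rates alone cannot show.

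This needs no new data and no change in sample size: only plan wording and extra table columns. The downside is bounds that may look wide. The text should also state the limits: bounds add nothing when attrition rates are equal, and re-weighting corrects only for observed characteristics.
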